**9.3 Recruitment of Potential Participants:**

- *Describe when, where, and how potential participants will be recruited.*
- *If the study involves the recruitment of participants from Divisions/Departments other than the PI's or Co-Investigators' Division/Department, describe how potential participants will be introduced to the study (e.g. telephone call, email, letter, personal introduction by treating physician). NOTE: It is best practice for the initial contact to be initiated by an individual with a clinical relationship with the potential participant. If this is not possible, and to satisfy HIPAA requirements, the initial contact must be made by a study team member who is an agent of CM.*
- *Upload any recruitment materials, including telephone scripts, in the myIRB application, Recruitment Materials section. For advertisements, attach the final copy of printed advertisements. When advertisements are taped for broadcast, attach the final audio/video tape or transcript. Wording of the advertisement may be submitted prior to taping to preclude re-taping because of inappropriate wording, provided the IRB reviews the final audio/video tape.*

## SHORT TITLE: Lactation at Work

- *If recruitment strategy involves contacting individuals multiple times, describe how frequently and in what manner individuals will be contacted and the maximum number of attempted contacts for any one individual.*

Subjects will be from CMKC Residents and Fellowships

Subjects will be primarily self-identified for the institution, through Graduate Medical Education there is a more focused approach by filtering notifications to just female identifying residents to remind them of the resource. Word of mouth from current users is also an important aspect to recruit participants as study grows.

Material provided during recruitment and to participants include the following:

Existing Policy and Procedures information

Lactation resource page which includes education resources

Willow product information

Utilization of internal communication platforms such as university calendar and e-newsletters

Fliers distributed in lactation rooms

Users will not be paid for their participation but will be allowed to keep the devices.

Per the Human Subjects Training the reviewers will follow the permissible recruiting regarding preparatory to research for any in person recruiting events targeted towards individuals that disclose they are pregnant or planning for pregnancy.

## 10.0 Surveys and Psychometric Testing:

- *Describe any surveys or psychometric testing that will be conducted as part of the study. Address whether the instruments used have been previously validated.*

## SHORT TITLE: Lactation at Work

- *List the names of each instrument (survey, questionnaire, test, etc). Upload copies of any surveys, psychometric tests, or other instruments that will be administered for research purposes in the myIRB application, Other Attachments section.*

INTAKE SURVEY – expectation and goals for lactation experience, demographics and knowledge of lactation from previous experiences.

MONTHLY SURVEY – changes to lactation practices, current volume, frequency and satisfaction.

OUTTAKE SURVEY – final experience input, expectations vs reality, total length of time pumping and providing milk

## 11.0 Additional Study Activities

**11.1** *Provide a description of all research activities beyond surveys and psychometric testing that are being performed and when they will be performed, including activities being performed to monitor for safety or minimize risks. Address:*

*N/A*

**11.2** *Blood and Other Specimen Collection:*

*N/A*

## 12.0 Follow-up

- *Describe the follow-up schedule, what data will be collected during this period, and how the data will be collected (e.g. telephone, email with link to data entry site, clinical chart review).*

No current plans for long-term follow-up

## 13.0 Genetic Analysis Information

*N/A*

## 14.0 Sharing of Results with Participants

N/A

## 15.0 Risks to Participants\*

**15.1** *List the research risks. Research risks are any potential physical, psychological, social, legal, privacy, confidentiality risks or economic harms that may come from participating in the study. This does not include the risk of any procedures conducted as part of standard care.*

- *Where applicable, describe the probability, magnitude, duration, and reversibility of the risks.*
- *Describe the measures taken to minimize these risks as this will be useful for the IRB in making their risk/benefit determination.*
- *If collecting or accessing sensitive data which may pose legal, economic, or reputational harm, describe this risk in detail.*

**15.2** *Indicate whether the researchers believe the risks involved in this study are minimal, or if the study poses greater than minimal risk of harm to participants.*

**15.3** *If applicable, indicate which activities may have risks to the participants that are currently unforeseeable.*

**15.4** *If applicable, indicate which activities may have risks to an embryo or fetus, should the participant be or become pregnant.*

**15.5** *If applicable, describe risks to others who are not participants (e.g. pregnant partner of a male participant)*

There is minimal risk to participants other than normally occurring risks when pumping milk. These include low supply, infection, or stressors that can lead to individual's cessation of pumping. The study team will work to provide education on the device and access to lactation education to minimize risk.

## 16.0 Potential Benefits\*

**16.1** *Describe the potential of any direct benefits that individuals may experience from taking part in the research. Include the probability, magnitude, and duration of the potential benefits as this will be useful to the IRB in making their risk/benefit determination.*

*There is substantial benefit to participants, we are anticipating that participants will experience more autonomy and success with pumping at work, ability to pump longer, improved work-life integration. There are numerous health benefits for both participant and infant as outlined in the literature study included above which increase over time providing milk. Participants gain access to equipment that is currently at a higher price point compared to the free devices covered by insurance.*

**16.2** *Describe the potential of any benefits to society/science or others related to the possible knowledge gained.*

There is substantial benefit for society and science. Continued evidence for the benefit for supporting lactation for new mothers in the workplace can support continuing trends towards better and normalized support for others.

## **17.0 Investigator Assessment of Risk/Benefits Ratio\***

**17.1** *Please provide an assessment of risk and benefits in the table below. Note, the IRB makes the final determination based upon responses in the two preceding sections.*

Select as applicable:	Pediatric Risk Category:	
	Category 1	Research not involving greater than minimal risk (45 CFR §46.404 and 21 CFR §50.51)
	Category 2	Research involving greater than minimal risk but presenting the prospect of direct benefit to the individual participants. (45 CFR §46.405 and 21 CFR §50.52)
	Category 3	Research involving greater than minimal risk and no prospect of direct benefit to individual participants, but likely to yield generalizable knowledge about the participant's disorder or condition. (45 CFR §46.406 and 21 CFR §50.53)
	Category 4	Research not otherwise approvable which presents an opportunity to understand, prevent, or alleviate a serious problem affecting the health or welfare of children. (45 CFR §46.407 and 21 CFR §50.54)
Select if applicable:	Adult Risk Category:	
	Not Greater than Minimal Risk	
	Greater than Minimal Risk	

## **18.0 Payment, Reimbursement and Tangible Property provided to participants\***

Is payment, reimbursement, or tangible property part of the study?

Yes       No *(If No, delete the following subsections)*

**18.1 Payment to Participants:** *If providing payment for participation (e.g. cash equivalent for participation, payment for time off work), select the form of payment:*

- Gift card
- Prepaid Merchant Gift Card: (Merchant: \_\_\_\_\_)
- e-Gift card
- Other: \_\_\_\_\_

*Note: "Prepaid Merchant Gift Card," "e-gift card," and "Other" options require approval by Research Administration. Upon submission in myIRB, ORI staff will initiate the Research Administration approval process.*

**Payment Schedule:** *Describe the payment schedule (if the payment schedule is involved, consider using a table to display this information) including:*

- *The total amount anticipated*
- *The study time points when payments will be made and the amount of compensation at those time points.*
- *To whom payments will be made (i.e. to participants, to parents/LAR, or will this be based on some criterion such as age of participant).*
- *If total amount of payment and/or tangible property for an individual participant may exceed \$600, include plans for the collection of Social Security Number (SSN) or Individual Tax Identification Number (ITIN) as required by CM policy.*

**18.2 Reimbursement:** *If providing reimbursement (repayment to research participants and/or their families to cover out-of-pocket expenses they incur), select the form of reimbursement:*

- Gift card
- Other: \_\_\_\_\_

**18.3 Tangible Property:** *If providing tangible property or any item of value given for participation (e.g. a toy, a tote bag, a water bottle, an electronic device), describe:*

- *The item(s) to be given.*
- *How and when the item(s) will be distributed*
- *The estimated total maximum value of the item(s). If the total value is \$100 or more, provide a plan for tracking the items and value and how you will report this to Research Administration at the end of the year for 1099 purposes.*
- *If the estimated total maximum value of payment and/or tangible property provided to an individual participant may exceed \$600, include plans for the collection of Social Security Number (SSN) or Individual Tax Identification Number (ITIN) per CM policy.*

We will provide a Ceres Chill with each willow pump to allow moms the ability to keep milk cold throughout the work day without needing a fridge. The item will be distributed at the beginning of the study with the willow pump. The maximum value of the item is \$70.00. Willow INC is providing a Willow GO wearable Pump. The maximum value of this item is \$349.99.

## 19.0 Compensation for Research-Related Injury

N/A

## 20.0 Economic Burden to Participants

N/A

## 21.0 Parental Permission and Adult Consent Process\*

### 21.1 Indicate below all methods of Permission/Consent that will be used in this study.

- *If the study includes multiple study groups, be sure to indicate which method is being used with each group.*
- *If requesting a Waiver of Documentation, a complete Waiver, or an Alteration, complete the required addendum at the end of this document.*

#### Written Informed Permission/Consent

Written informed permission of parent/LAR for pediatric participants

Study group(s) to which this method applies:

Written informed consent of adult participants

Study group(s) to which this method applies: All participants

SHORT TITLE: Lactation at Work

Informed consent will be obtained at the beginning of the survey process at device handoff, individuals will complete the consent form which will trigger the survey timing.

**Non-English-Speaking Subjects**

It is unknown if there will be any non-English speakers enrolled in the survey, the institution hires and trains individuals that do not speak English as a primary language, but they are expected to be able to be fluent in English for their training and employment. If a subject is minimally fluent in English, we will work with the Human Resource office to navigate communication barriers.

**Written informed consent of participants turning 18**

This includes the continued access to and use of their PHI by the study team.

Study group(s) to which this method applies:

**Waiver of Documentation of Permission/Consent**

Permission/Consent form provided but signature will **NOT** be obtained (e.g. verbal consent)

Must complete [Addendum A: Waiver of Documentation of Permission/Consent](#)

**Waiver of written documentation of permission of parent/LAR for pediatric participants**

Study group(s) to which this method applies:

**Waiver of written documentation of consent of adult participants**

Study group(s) to which this method applies:

**Waiver of written documentation of consent of participants turning 18**

Study group(s) to which this method applies:

**Waiver or Alteration of Permission/Consent**

## SHORT TITLE: Lactation at Work

Parent/LAR permission/adult consent will **NOT** be obtained, or an alteration to an element(s) of consent.

**Must complete [Addendum B: Waiver of Permission/Accent/Consent](#)**

**Waiver/Alteration of permission of parent/LAR for pediatric participants**

Study group(s) to which this method applies: Moms babies date of birth. The consent form will be provided electronically for them to indicate agreement and consent.

**Waiver/Alteration of consent of adult participants**

Study group(s) to which this method applies: Primary participants, moms. The consent form will be provided electronically for them to indicate agreement and consent. All participants

Informed consent will be obtained at the beginning of the survey process at device handoff, individuals will complete the consent form which will trigger the survey timing.

### **Non-English-Speaking Subjects**

It is unknown if there will be any non-English speakers enrolled in the survey, the institution hires and trains individuals that do not speak English as a primary language, but they are expected to be able to be fluent in English for their training and employment. If a subject is minimally fluent in English, we will work with the Human Resource office to navigate communication barriers.

**Waiver/Alteration of consent of participants turning 18**

Study group(s) to which this method applies:

### **Additional Methods**

**Obtaining permission/assent/consent of non-English speaking parents or participants**

Must compete [Addendum C: Non-English Speaking Participants](#)

Study group(s) to which this method applies:

**Surrogate decision maker consent to be used when adults are not capable of consenting for themselves**

Must complete [Addendum D: Surrogate Decision Maker Consent](#)

Study group(s) to which this method applies:

**21.2 Permission/Consent/Consent at 18 Discussion:** *If selected options for "Written" or "Waiver of Documentation" above, describe below how the informed permission/consent discussion will be conducted. Describe:*

- *Where and when the discussion will take place.*
- *Steps that will be taken to minimize the possibility of coercion or undue influence.*
- *Any supplemental materials that will be used to enhance the discussion (e.g. videos, eConsent, educational pamphlets).*
- *Any measures that will be taken to ensure that parent(s)/LAR have adequate time to ask questions and decide if they will permit their child to participate in the study (e.g. providing copy of permission form in advance of visit).*
- *How comprehension of the permission form will be verified (e.g. teach back).*
- *If obtaining permission via telephone, confirm CM research policy will be followed.*
- *Process to ensure ongoing consent during the study.*

**21.3 Documentation of Permission/Consent/Consent at 18:** *If selected "Written" options above, explain how informed permission will be documented. Describe:*

- *Whether CM Research Policy "10.04 Obtaining Permission/ Assent/ Consent" and "Research Documentation in the Electronic Health Record" will be followed. If not, describe whether and how permission of the parent(s)/LAR will be documented in writing.*
- *Whether e-Consent will be used to document permission (non-FDA regulated studies only).*

**21.4 Identification of participants turning 18:** *Explain the process for tracking participants to ensure that consent is obtained to continue participation once they turn 18 years of age.*

## 22.0 Assent of Pediatric Participants

**22.1 Select the option(s) that apply to the study:**

**Assent of pediatric participants WILL BE SOUGHT following assessment of ability to assent.**

**Obtaining assent of pediatric participants is NOT POSSIBLE due to:**

- The capability of the participants (considering the ages, maturity, physical and/or psychological state) is so limited that they cannot reasonably be consulted.*
- The intervention or procedure involved in the research holds out a prospect of direct benefit that is important to the health or well-being of the participants and is available only in the context of the research.*

**Obtaining assent of pediatric participants is NOT PRACTICLE given the context of this study** (e.g., minimal risk, no direct contact with participants).  
Must complete [Addendum B: Waiver/Alteration of Permission/Assent/Consent](#)

## 23.0 HIPAA and Confidentiality

HIPAA regulations apply to this study if the data used or accessed relates to:

- The past, present or future physical or mental health or condition of an individual;
- The provision of health care to an individual; **OR**
- The payment for the provision of health care, **AND**

identifies the individual or for which there is a reasonable basis to believe it can be used to identify the individual.

### 23.1 HIPAA Authorization

*Select all applicable methods of HIPAA Authorization that apply to this study.*

SHORT TITLE: Lactation at Work

Full Written HIPAA Authorization will be obtained (within the p/a/c form or standalone form)

Partial Waiver of HIPAA Authorization (e.g. waiver for recruitment and pre-screening purposes only)

**Must complete [Addendum E: Waiver/Alteration of HIPAA Authorization](#)**

*a) Describe what PHI must be accessed for recruitment/pre-screening purposes prior to obtaining HIPAA Authorization..*

Alteration of HIPAA Authorization (some but not all required elements of an Authorization are present, e.g. signature will not be obtained)

**Must complete [Addendum E: Waiver/Alteration of HIPAA Authorization](#)**

*a) Describe which proposed elements to be altered.*

Waiver of HIPAA Authorization (authorization will NOT be obtained)

If Other, explain:

**23.2** Specify the PHI for which accessing (“viewing”) or recording (“writing down”) is necessary for the purpose of this research:

*To minimize risks, only the minimum necessary identifiable data should be accessed/viewed and/or recorded/written down.*

PHI	Accessed Only	Recorded
1. Name/Initials		
2. All elements of date (except year) directly related to an individual (e.g. date of birth, admission date, discharge date, date of death)		
3. Medical record number		
4. Account number		
5. Health plan identification number		
6. Social Security Number		
7. Device identifiers and serial number		
8. Certificate/License number		
9. Telephone number		
10. Fax number		
11. Email addresses		

SHORT TITLE: Lactation at Work

12. Web addresses (URLs); Internet IP addresses		
13. Street address, city, county, precinct, zip code or equivalent geographical codes		
14. Full face photographic images and any comparable images (this includes use of video recordings via Teams)		
15. Biometric identifiers, including finger and voice print (this includes recorded Teams audio)		
16. Vehicle identifiers and serial numbers, including license plate number		
17. Any other unique identifying number, characteristic or code that may help identify individual participants including their initials (e.g. student or employee ID number )		
18. Elements of date, including year, for persons 90 years or older		
19. Other:		

**23.3** *Indicate how the research team will protect the confidentiality of participant data during storage, use, and transmission (e.g. training, authorization of access, password protection, encryption, physical controls, and separation of identifiers and data [master list]). Remember: Sensitive CM data, including research data, must be stored on a file server on the CM network domain – not on a workstation hard drive.*

Data will be stored in redcap until study concludes with monthly data reports delivered via secure email to those included in the DUA. Data from Willow will be provided by serial number for data matching to Redcap data. Redcap is designated for research purposes at the academic medical center. Data will be quantitatively analyzed via SAS by the biostatistical partner, contracted through the institution. Willow will provide

Individual users will be deidentified data and enrolled in the study by serial number for data matching with Willow application data.

Investigators will have access to the data for analysis and aggregate reporting purposes. Data stored on secure internal network drives.

SHORT TITLE: Lactation at Work

Investigators are responsible for receipt and any transfer of the data through secure network tools.

**23.4** *State whether a Certificate of Confidentiality has been issued for this study. Certificates are automatically issued for NIH funded research per NIH policy. For non-federally funded research involving identifiable, sensitive information, investigators may apply for a Certificate if desired. See the NIH website on Certificates of Confidentiality for more details.*

There has not been issued a Certificate of Confidentiality for this study.

- 

**24.0 Provisions to Protect the Privacy Interests of Participants\***

**24.1** *Describe the steps that will be taken to protect participant's privacy during recruitment and while obtaining permission/assent/consent. For example, best practice is to obtain permission/assent/consent in a separate area where a private conversation can be had. If this is not possible, be sure to explain what steps will be taken to provide as much privacy as possible.*

Participants will be deidentified in the survey using a assigned study ID.

This study ID will allow us to link their survey data and their serial number of the Willow Go pump to match data from the surveys to the data from Willow. To protect anonymity, individual data for the post survey will be reviewed to ensure there are not any serious triggers in the final comments that would indicate concerns with the program, but the data reviewed cumulatively and as deidentified.

**24.2** *Describe what steps you will take to make the participant feel at ease with the research situation in terms of the questions being asked and the procedures being performed. "At ease" does not refer to physical discomfort, but the sense of intrusiveness a participant might experience in response to questions, examinations, and procedures.*

Surveys will be completed via RedCap. Individuals that reach out to participate will be provided information on pumping with the Willows and

the informed consent form at the beginning. Participants do not have to answer any questions they do not feel comfortable.

**24.3** *Indicate how the research team is permitted to access any sources of information about the participants and how the research team will protect the confidentiality of the data.*

Biographic data will be collected through the RedCap survey. And only collected at planned intervals (quarterly) to assess midpoint measurements as deidentified combined and/or aggregate data.

## 25.0 Withdrawal of Participants\*inclusio

**25.1** *Describe anticipated circumstances, under which participants will be withdrawn from the research without their consent.*

*A subject can withdraw at any time during the study without being required to return the device.*

**25.2** *Describe procedures that will be followed when participants are withdrawn from the research, including data retention plans or partial withdrawal from procedures with continued data collection.*

*If the subject leaves to the institution (institutional email is deactivated) they will be terminated from the study unless they notify the institution of the transition to remain in the study and provide a new email.*

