Final experience input, expectations vs reality, total length of time pumping and providing milk		X	X

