## 28.0 Statistical Analysis\*

**28.1** *Describe the data analysis plan, including any statistical procedures or power analysis.*

We plan to examine changes in professional fulfillment and burnout using repeated measures t-test. We also plan to utilize descriptives and qualitative comments to show evidence of whether the Willow device helps the participant reach their lactation goals.

**28.2** *Describe how the sample size for the study was determined (e.g. formal sample size calculation, convenience sampling). To minimize the risks associated with a possible breach of confidentiality, appropriate sample size calculations limit the amount of patient data being recorded to the amount necessary to answer the research question.*

For all the planned analyses, having a study sample of 125-150 will be sufficient. This presents the goal for each site to have 20-25 participants over the next two years.

•
---

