**N/A**

**31.1** *In addition to the Principal Investigator, which individual or group will be responsible for monitoring the data and safety for this study?*

- Sponsor or Sponsor Designee (including the Sponsor CRO)
- Data and Safety Monitoring Board (DSMB) or Data Safety Monitoring Committee (DSMC)
- Independent Monitor (s)
- Internal Committee at CM
- Other: \_\_\_\_\_

**31.2 Data Safety Monitoring Plan:** *If a DSMB charter or other external monitoring plan is available, upload in the myIRB application, Other Attachments section. If such a charter/plan is not available, describe:*

- *The plan to periodically evaluate the data collected regarding both harms and benefits to determine whether participants remain safe. The plan might include establishing a data monitoring committee and reporting data monitoring committee findings to the IRB and the sponsor. For NIH funded research, see requirements for [Data and Safety Monitoring](#)*
- *What data are reviewed, including safety data, untoward events, and efficacy data.*
- *How the safety information will be collected (e.g. with case report forms, at study visits, by telephone calls with participants).*
- *The frequency of data collection, including when safety data collection starts.*
- *Who will review the data.*
- *The frequency or periodicity of review of cumulative data.*
- *The statistical tests for analyzing the safety data to determine whether harm is occurring.*
- *Any conditions that trigger an immediate suspension of the research.*

*Participation is fully voluntary and there will be no undue influence to pump if a participant is unhappy or unable to use the devices, individuals will need to let us know when they are done so Investigators can send them the final survey and remove them from the monthly send. Our survey will ask questions about what made them*

*stop pumping and there is an open text box for those that would like to provide any detail about their experience.*

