Individuals will be surveyed monthly on basic data but will be asked to assess if they are satisfied with the device, and utilization, Investigators will ask users to let us know when they cease pumping so Investigators can send the outtake survey (probably link it to the monthly survey) and then Investigators will end monthly survey Data reviewed monthly will include number of active users in the study, volume of milk and frequency of pumping. Quarterly review of satisfaction with Willow devices and utilization of other resources will be reviewed in aggregate. Early cessation in the study will be reviewed for qualitative responses to determine trends in cessation. Project Investigators will review monthly report and provide to Willow Investigators will review data once a final survey has been completed and overall data quarterly including any anonymous comments, if there are concerns about safety in the comments, investigators will ask individuals to notify us immediately so Investigators can reassess.

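### Final outtake answers will be missing for leavers who give no new email and for women who stop silently, and no substitute source is named

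*Protocol*

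**What the plan says.** Four parts of the protocol bear on whether the final outcome is collected.

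- **Aim.** Section 2.1 intends to follow users until their pumping ends. It asks whether access to the pump improves the lactation experience and the meeting of duration goals. Section 7.1 restricts eligibility to women who give birth during a residency or fellowship at the institution.
- **Leaving the institution.** Section 25.2 sets the default for participants whose work account closes: "they will be terminated from the study unless they notify the institution of the transition to remain in the study". To use this exception she must also supply another address. Section 12.0 plans no long-term follow-up.
- **Trigger for the final survey.** Section 31.2 states that "individuals will need to let us know when they are done so Investigators can send them the final survey" and, further on, that "Investigators will ask users to let us know when they cease pumping so Investigators can send the outtake survey". The only automation mentioned is in a parenthesis: "send the outtake survey (probably link it to the monthly survey".
- **Where the outcome sits.** Section 10.0 describes the outtake survey as covering "final experience input, expectations vs reality, total length of time pumping and providing milk". The Table of Events in Section 5.2 marks the same content for the monthly survey as well.

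Section 28.1 then relies on "descriptives and qualitative comments to show evidence of whether the Willow device helps the participant reach their lactation goals".

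**The concern.** Both rules make the final answer depend on the participant taking the initiative. A trainee's departure is foreseeable, and the default on departure is to end participation, for a reason that has nothing to do with pumping. A woman who stops and disengages receives no outtake survey unless the tentative link to the monthly survey is built and she answers that survey.

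This missingness is plausibly related to outcome. Section 26.2 itself recognises that participants whose goals are not met may see the data as a threat to their reputation, which gives them a reason not to announce that they have stopped. The study has one group, and Section 2.1 compares it with national figures, so there is no concurrent arm in which a similar loss might partly cancel. These are collection rules fixed in the protocol, and no analysis plan can recover answers that were never collected.

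**Working it through.** The protocol gives no expected completeness, and the 125 to 150 participants in Section 28.2 come without an allowance for loss, so there is no figure of the plan's own to reproduce. The check sets the rules against each other and then sizes the possible effect.

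**1. Which data survive under each route**

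- *Leaver who gives a new email:* stays in the study; nothing is lost.
- *Leaver who gives none:* terminated. No exit survey or other contact is described. Monthly surveys up to that date remain. The protocol does not say whether device data continue to be supplied.
- *Silent stopper:* no outtake survey. Earlier monthly surveys remain, including the goal question (Section 5.1). Device data linked by serial number (Sections 5.1 and 26.1) could show the last Willow use, but not other pumps, direct feeding or her final judgement on her goal.

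**2. Share exposed to the termination rule**

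Assumptions (not in the documents): 36-month programmes, births spread evenly over training, and pumping for L months. Share still pumping when training ends = L/36.

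- L = 7: 7/36 = 19%
- L = 10: 10/36 = 28%
- L = 12: 12/36 = 33%

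This is exposure to the rule, not a loss rate, because women who supply a new email are retained.

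**3. Effect on reported goal attainment**

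Inputs: observed attainment p = 0.75, the figure reported for the similar programme in the literature update of Section 3.3. National attainment is 1 − 0.60 = 0.40, from the statement in Section 3.3 that 60% of mothers miss their goal. The share missing, m, is assumed to be 10% to 40%.

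- Lowest possible true rate = p(1 − m)
- Highest possible true rate = p(1 − m) + m
- True rate if missing women attain at 40% = p(1 − m) + 0.40m, so the overstatement is (0.75 − 0.40)m = 0.35m

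| m | Lowest | Highest | Missing attain 40% | Overstatement |
|---|---|---|---|---|
| 10% | 67.5% | 77.5% | 71.5% | 3.5 points |
| 20% | 60.0% | 80.0% | 68.0% | 7.0 points |
| 30% | 52.5% | 82.5% | 64.5% | 10.5 points |
| 40% | 45.0% | 85.0% | 61.0% | 14.0 points |

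The highest-rate column shows the opposite case: if every missing woman had met her goal, 75% would understate the truth by 0.25m, or 2.5 to 10 points. The lowest bound reaches the 40% national figure only at m = 1 − 0.40/0.75 = 46.7%.

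**4. Direction**

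Silent stoppers have probably missed their goals more often than women who report, so losing them would tend to raise reported attainment. Women terminated on leaving are still pumping, and the exposed share rises with L, so they tend to be longer pumpers. Losing them may shorten observed duration or lower attainment. The two effects pull in opposite directions, and the protocol gives no basis for netting them.

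**The case against.** The strongest reply is that little is truly lost. One message with a new address keeps a leaver in the study. Section 31.2 already contemplates linking the outtake survey to the monthly one and plans a review of early cessation. The Table of Events puts "Final experience input, expectations vs reality, total length of time pumping and providing milk" under the monthly survey too, and device data are linked by serial number rather than by email. All of this stands, and it limits the point to partial loss. It does not remove it. The link is tentative, monthly surveys also fail when the email closes or the woman goes quiet, and nothing says that these sources replace a missing outtake survey.

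Three stronger readings are tempting, and the documents do not support them.

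- A reader might infer that outcomes are lost for graduates in general. The exception in Section 25.2 and the monthly and device data rule that out.
- A reader might infer that goal attainment must be inflated. If 20% or 30% were missing and every one of them had failed, a true 60% would appear as 0.60/0.80 = 75% or 0.60/0.70 = 86%. That assumes no missing woman met her goal, which cannot be presumed of leavers who are still pumping.
- A reader might fault the absence of censoring rules or sensitivity analyses. Those commonly belong in a statistical analysis plan, which is not at hand.

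The three-year close adds little. With one year of device distribution and up to three years of data collection (Section 2.1), even late enrollees have about two years, and in the similar programme 31% pumped for ten months or more.

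**Conclusion.** The point holds as a defect in data collection. Sections 25.2 and 31.2 make the final outtake answers depend on participant initiative, which conflicts with the aim in Section 2.1 of following users to the end of pumping. Those answers will be missing for leavers who give no new email and for silent stoppers, and partial information up to last contact is not designated as a substitute.

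The loss is plausibly related to outcome, but its net direction is not established. The 3.5 to 14 point overstatement rests on an observed 75%, missing women attaining at 40%, and an assumed 10% to 40% missing. The 19% to 33% exposed to the termination rule rests on three-year programmes, evenly spread births and 7 to 12 months of pumping. The change should be made before enrolment. It does not invalidate the study.

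**What to change.** - Record a personal email at consent and send surveys to it by default.
- Amend Section 25.2 so that leaving the institution does not end data follow-up unless the woman withdraws.
- In Section 31.2, replace the tentative link with a firm rule: the outtake survey goes out automatically when a monthly survey reports that pumping has stopped, and after a set number of missed monthly surveys.
- State that when no outtake survey is returned, the last monthly survey is used, supplemented by the device log. Note that the log shows Willow use only, so a gap may mean a change of pump rather than stopping.
- State whether device data continue after a woman leaves the institution, and reconcile Sections 2.1, 25.2 and 31.2.

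The cost is one more contact identifier of a type that Section 23.2 already records, with a slightly larger privacy footprint, and some REDCap automation. How the fallback data are analysed can be left to the statistical analysis plan.
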